4.4. Patients Excluded from the Analysis and Patients with Special Background

4.4.1. List of patient numbers of patients excluded from the analysis and patients with special background

- Patients for summarization: Patients excluded from the safety analysis, patients excluded from the effectiveness analysis, and patients included in the safety analysis

4.4.1.1. Selection of patients excluded from the safety analysis

Patients excluded from the safety analysis will be selected by reason for exclusion and the following items will be presented (Table 4.1.1).

No	Reason for exclusion	Items to be displayed
1	No dose received	Registration number
2	No visit made	Registration number, reason for discontinuation of the survey, date of discontinuation of the survey, start date of treatment, end date of treatment

4.4.1.2. Selection of patients excluded from the effectiveness analysis

Patients excluded from the effectiveness analysis will be selected by reason for exclusion and the following items will be presented (Table 4.1.2).

No	Reason for exclusion	Items to be displayed
1	Cannot be determined	Registration number

4.4.1.3. Selection of patients with special background

Among the patients included in the safety analysis, patients with special background will be selected and their registration numbers will be presented (Table 4.1.3).

No	Special background	Description
1	Children	Patients aged <15 years
2	Pregnant women and nursing mothers	Pregnant patients
3	Hepatic impairment	Patients with concurrent hepatic impairment
4	Renal impairment	Patients with concurrent renal impairment
5	Respiratory disease	Patients with concurrent respiratory disease

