After administration of LipaCreon started, the information will be collected until the end of March 2018. First 52 weeks from the start will be observation period and 53 weeks and onwards will be follow-up period.

8. Survey items

(1) Items required for specifying the patient:

Patient ID No.

(2) Patient background:

Sex, presence or absence of pregnancy/breast feeding (female only), date of birth or age, inpatient/outpatient classification, start date of administration, concomitant diseases (hepatic, renal or respiratory disorders, other), history of disease, history of allergy, prior treatment drug (digestive enzyme product)

(3) Administration status of LipaCreon:

Daily dose, administration period, drug regimen compliance, the reason for a change in dose

(4) Administration status of concomitant drugs:

[Other digestive enzyme products]:

Presence or absence of treatment with other digestive enzyme product, drug name, daily dose, administration period

[Other concomitant drugs]:

When additional information is required at the onset of adverse event, etc., the following information is investigated:

Presence or absence of information for the concomitant drugs, drug name, administration route, reason for use, daily dose, administration period

(5) Adverse events

All the undesirable or unintended diseases, or their symptoms, signs or abnormal changes in laboratory test values, etc. that have occurred in the patients administered LipaCreon are handled as the adverse events regardless of the causal relation to LipaCreon. The adverse events whose causal relation to LipaCreon is not deniable are handled as adverse reactions.

Concerning the adverse events that occur from the start to the completion of administration of LipaCreon, the following items are investigated. In principle, the course of adverse event is observed until the event is judged by the physician in charge of registry to cause no clinical problem.

Diseases, symptoms, signs or abnormal changes in laboratory test values which were attributed to the cystic fibrosis, will not be regarded as adverse event, but as the events attributed to cystic fibrosis.(please refer to [(6) Events attributed to cystic fibrosis])

1) Presence or absence of adverse event 2) Name of adverse event

3) Date of onset 4) Seriousness 5) Administration of LipaCreon

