2.3. Definitions of Patient Demographic Factors and Indicators of Treatment Status

No	Patient demographic factor	Description
1	Sex	Male, female, unknown/unspecified
2	Pregnancy status	Not pregnant, currently pregnant, unknown/unspecified
3	Breastfeeding status	Not breastfeeding, currently breastfeeding, unknown/unspecified
4	Age category-1	<15 years old, ≥15 years old, unknown/unspecified
5	Age category-2	<6 years old, ≥6 years old and <12 years old, ≥12 years old and <18 years old, ≥18 years old, unknown/unspecified
6	Age	Actual value
7	Body height category-1	<140 cm, ≥140 cm and <150 cm, ≥150 cm and <160 cm, ≥160 cm and <170 cm, ≥170 cm and <180 cm, ≥180 cm, unknown/unspecified
8	Body height	Actual value
9	Body weight category-1	<30 kg, ≥30 kg and <40 kg, ≥40 kg and <50 kg, ≥50 kg and <60 kg, ≥60 kg and <70 kg, ≥70 kg and <80 kg, ≥80 kg, unknown/unspecified
10	Body weight	Actual value
11	BMI category-1	<18.5, ≥18.5 and <25, ≥25, unknown/unspecified
12	BMI	Actual value Body weight / (Body height/100)**2 The value will be indicated to two decimal places rounded from three decimals.
13	Inpatient/outpatient category	Inpatient, outpatient, unknown/unspecified
14	Presence or absence of concurrent diseases	Absent, present, unknown/unspecified
15	Presence or absence of concurrent hepatic impairment	Absent, present, unknown/unspecified
16	Presence or absence of concurrent renal impairment	Absent, present, unknown/unspecified
17	Presence or absence of concurrent respiratory disease	Absent, present, unknown/unspecified
18	Presence or absence of other concurrent diseases	Absent, present, unknown/unspecified
19	Presence or absence of previous diseases	Absent, present, unknown/unspecified
20	Presence or absence of allergy history	Absent, present, unknown/unspecified
21	Presence or absence of previous drugs	Absent, present, unknown/unspecified
22	Presence or absence of concomitant digestive enzyme preparations	Absent, present, unknown/unspecified
No	Indicator of treatment status	Description
23	Dosage form	Granule, capsule, granule + capsule, unknown/unspecified

No	Patient demographic factor	Description

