Patient number lists will be prepared for the following: Patients with adverse drug reactions; patients with adverse drug reactions whose outcome is "not resolved," "with sequelae," "fatal," or "unknown;" patients who have adverse drug reactions after the completion of treatment; pediatric (aged <15 years) patients with adverse drug reactions; pregnant patients with adverse drug reactions (those who are pregnant during the duration of treatment with Lipacreon); patients with adverse drug reactions who have hepatic impairment; patients with adverse drug reactions who have renal impairment; and patients with adverse drug reactions who have respiratory disease (Table 2.1.5.2).

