4.3.1.1. Degree of overall improvement

For patients included in the effectiveness analysis, the number and percentage of patients by evaluated overall improvement at Week 24, Week 52, and the time of last evaluation will be calculated (Table 3.1.1.1).

For patients included in the effectiveness analysis (patients completing the 52-week treatment), the number and percentage of patients by evaluated overall improvement at Week 24 and Week 52 will be calculated (Table 3.1.1.2).

For patients included in the effectiveness analysis or patients included in the effectiveness analysis (patients completing the 52-week treatment), a list of patients concerning the degree of overall improvement will be prepared for patients with special background (children, pregnant women and nursing mothers, hepatic impairment, renal impairment, respiratory disease). Item to be output will be determined according to the analysis table and figure output plan (Table 3.1.1.3.1, Table 3.1.1.3.2, Table 3.1.1.3.3, Table 3.1.1.3.4, Table 3.1.1.3.5, Table 3.1.1.4.1, Table 3.1.1.4.2, Table 3.1.1.4.3, Table 3.1.1.4.4, and Table 3.1.1.4.5).

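### The special-background group for pregnant women and nursing mothers is selected on pregnancy alone, so a breastfeeding patient who is not pregnant is left off the list that names her

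*SAP*

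**What the plan says.** SAP 4.4.1.3 states that, within the safety analysis set, "patients with special background will be selected and their registration numbers will be presented (Table 4.1.3"). Five groups follow, each with a label and a description. The second is labelled "Pregnant women and nursing mothers" and described as "Pregnant patients".

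SAP 4.3.1.1 plans lists of overall improvement for patients with "special background (children, pregnant women and nursing mothers, hepatic impairment, renal impairment, respiratory disease"). In SAP Section 6, the titles of Table 3.1.1.3.2 (effectiveness set) and Table 3.1.1.4.2 (52-week completers) carry the same group name.

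The two conditions are separate variables in SAP 2.3. Item 2, pregnancy status, has the categories "Not pregnant, currently pregnant, unknown/unspecified". Item 3, breastfeeding status, has "Not breastfeeding, currently breastfeeding, unknown/unspecified". Protocol Section 8, item (2), collects "presence or absence of pregnancy/breast feeding (female only") as patient background.

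**The concern.** The label covers two kinds of patient and the rule selects one. A programmer who follows the rule will produce a list headed for nursing mothers from which they are absent unless they are also pregnant.

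The survey covers every treated patient because the population is very small and few were studied before approval. In such a survey the patient lists are the natural way to report the one or two people in a special group. The results could also disagree visibly: Table 1.2.1 could count a breastfeeding patient while the row of Table 4.1.3 that names nursing mothers is empty.

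**Working it through.** No arithmetic applies. The check is to compare label with rule, see whether another section supplies the missing half, and trace the outputs.

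**1. Label against rule in SAP 4.4.1.3.**

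| Group | Selected on | Rule covers the label? |
|---|---|---|
| Children | age under 15 | yes |
| Pregnant women and nursing mothers | pregnancy | first half only |
| Hepatic impairment | concurrent hepatic impairment | yes |
| Renal impairment | concurrent renal impairment | yes |
| Respiratory disease | concurrent respiratory disease | yes |

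**2. Can pregnancy status stand in for breastfeeding?** No. In SAP 2.3, item 2 has no breastfeeding category. A patient recorded as not pregnant under item 2 and currently breastfeeding under item 3 fails the rule. A patient who is both is selected, but because of the pregnancy.

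**3. Is the group defined elsewhere?** No other section of the SAP or protocol defines it. SAP 4.3.1.1 names it without a definition. That section leaves the items to be output to the output plan, but not the membership of the group.

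**4. Which outputs are affected?**
- Table 4.1.3: directly.
- Tables 3.1.1.3.2 and 3.1.1.4.2: by inference. SAP 4.3.1.1 uses the same five groups in the same order, and the effectiveness sets are subsets of the safety set (SAP 2.1, items 10 to 13), so the rule carries over without difficulty.
- Table 2.1.5.2: not a mislabelled list. SAP 4.2.1.5 announces "pregnant patients with adverse drug reactions (those who are pregnant during the duration of treatment with Lipacreon") and defines just that, with no mention of nursing mothers.

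**5. Where does breastfeeding still appear?** As a Section 2.3 factor it is tabulated in Table 1.2.1 (patient counts), Table 2.3.1.1 (adverse drug reaction incidence) and Tables 3.1.2.1 and 3.1.2.2 (improvement and effectiveness rate). It is not among the items set out for the adverse event list (Table 2.1.5.1) or for the cystic fibrosis patient lists (Tables 5.2.1.1 to 5.2.1.3). The aggregate tables would therefore count a nursing mother, but no patient list whose items the SAP specifies would identify her as one.

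**6. What data exist?** The protocol's survey schedule takes patient background only at the start of administration, so breastfeeding status is available at that point. Protocol Section 8, item (11), adds a separate investigation of pregnancies, including those found during the observation period, when the pregnancy becomes known and after the birth. It schedules no breastfeeding item.

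**The case against.** The strongest reply is that almost nothing is lost. Exposure, adverse drug reaction incidence and effectiveness by breastfeeding status are all tabulated in aggregate, Table 4.1.3 shows registration numbers only, and no inference depends on it. All of this stands and sets the size of the point.

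A second reply is that SAP 4.3.1.1 names nursing mothers in full and does not refer to 4.4.1.3, so the two effectiveness lists might be programmed correctly. That is possible, and the effect on those tables is therefore conditional. But the only rule available to a programmer is the one in 4.4.1.3.

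Four stronger readings are tempting, and the documents do not support them:
- A reader might infer that a breastfeeding patient appears in no special-background selection. She may be listed under another heading, for example respiratory disease. What is true is that breastfeeding does not place her in any of them.
- A reader might infer that the survey would report no exposure in nursing mothers. Table 1.2.1 would still count them.
- A reader might take the adverse drug reaction list in Table 2.1.5.2 as a further error. It does not carry the nursing-mothers label and does what it says.
- A reader might suppose that a rule covering breastfeeding throughout treatment needs only new wording. The planned data support status at the start only.

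**Conclusion.** The rule contradicts its own label, and the point holds for Table 4.1.3 on the face of the SAP. For Tables 3.1.1.3.2 and 3.1.1.4.2 it holds on the assumption that they use the only definition given.

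The consequence is minor: descriptive lists change, and no test or estimate does. The documents do not give the number of patients who are breastfeeding and not pregnant. A range of 0 to 2 is assumed, against the 38 cystic fibrosis patients over ten years that the protocol cites. Whatever the number, the rule as written misses every one of them under this heading.

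**What to change.** In SAP 4.4.1.3, describe the second group as: patients who are currently pregnant or currently breastfeeding (Section 2.3, items 2 and 3, status at the start of treatment), or whose pregnancy is found during treatment. State in 4.3.1.1 that the same definition applies, so that Tables 4.1.3, 3.1.1.3.2 and 3.1.1.4.2 agree. Add that breastfeeding beginning during treatment is included only where it has been reported, because no visit schedules it.

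The cost is about one line in 4.4.1.3 and a cross-reference in 4.3.1.1, with a small change to the selection code. No new data collection is needed for status at the start of treatment. If the sponsor intends pregnancy only, the alternative is to rename the group and the two table titles accordingly.

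Adding a breastfeeding category to Table 2.1.5.2 is optional. It would help consistency but does not correct an error.

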4.5. Patients with Cystic Fibrosis of the Pancreas

4.5.1. Occurrence of events associated with cystic fibrosis of the pancreas

- Patients for summarization: Patients included in the safety analysis

4.5.1.1. Occurrence of events associated with cystic fibrosis of the pancreas

For patients included in the safety analysis, a list of reported events associated with cystic fibrosis of the pancreas will be prepared (Table 5.1.1).

4.5.2. List of patients with cystic fibrosis of the pancreas

- Patients for summarization: Patients with available case report forms

12	Outcome	Resolved, resolving, not resolved, sequelae, fatal, unknown

4.6. Attached Forms

4.6.1. Attached forms

- Patients for summarization: Patients with available case report forms

4.6.1.1. List of reported adverse drug reactions and infections [Attached Form 2]

The occurrence of adverse drug reactions and infections will be summarized.

Line

No	Item name	Description
1	Number of institutions surveyed	The same institution name will be regarded as 1 institution.
2	Number of patients surveyed	The separate volume for each reporting interval will be counted as the number of patients. If only 1 separate volume is locked, 1 separate volume will be regarded as 1 patient. If 2 separate volumes are locked at the same time, 2 separate volumes will be regarded as 1 patient. The total number of patients surveyed will be counted as the number of patients irrespective of separate volumes.
3	Number of patients with adverse drug reactions and number of adverse drug reactions	Adverse drug reactions corresponding to the number of patients surveyed (or each reporting interval) will be counted as the number of patients. If the same adverse drug reaction (PT) occurs repeatedly and is recorded multiple times, the adverse drug reaction will be summarized in the row of the period in which the firstly completed separate volume is counted. In addition, adverse drug reactions corresponding to the number of patients surveyed (total) will be counted as the number of patients.
4	Percentage of patients with adverse drug reactions	= Number of patients with adverse drug reactions / number of patients included in the safety analysis × 100
5	System organ class	MedDRA SOCs will be used. If the same patient experiences any adverse drug reaction (MedDRA SOC) multiple times, the patient will be counted once. Adverse drug reactions will be displayed in the SOC internationally agreed order.
6	Event name	MedDRA PTs will be used. If the same patient experiences any adverse drug reaction (MedDRA PT) multiple times, each event will be counted once. Adverse drug reactions will be displayed in the order of PT codes.

Row

No	Item name	Description
1	Survey period	See Section 2.1.

An unknown adverse drug reaction will be displayed with an asterisk (*) on its left side.

Novelty information (unknown or known) will be included in the information on MedDRA coding information provided by Mylan EPD G.K. Based on the novelty information, it will be determined whether an adverse drug reaction is unknown or not.

4.6.1.2. List of reported serious adverse events [Periodic safety report, Attached Form 2-2; Re-examination, Attached Form 10]

The occurrence of serious adverse events will be summarized. A list of serious adverse events will be prepared only for LPC02T.

The occurrence of serious adverse events will be summarized, as with Attached Form 2.

According to Appendix 2 (Attached Form 2-2) of the Notification No. 0325001 of the Safety Division, Pharmaceutical and Food Safety Bureau, MHLW and Notification No. 0325006 of the Evaluation and Licensing Division, Pharmaceutical and Food Safety Bureau, MHLW dated March 25, 2005, the number of unrelated serious adverse events will be summarized and displayed in [brackets] by MedDRA PT code.

4.6.1.3. Summary list of patients surveyed [Re-examination, Attached Form 3]

A summary list of patients surveyed will be prepared at the time of summarization for the re-examination.

Contents to be output will be specified separately in the written statistical analysis specification.

4.7. Additional Summarization for the Re-examination

- Patients for summarization: Patients with available case report forms and patients included in the safety analysis

4.7.1.1. Occurrence of adverse drug reactions and infections up to the time of approval [Re-examination, Attached Form 2 (New notification)]

The occurrence of adverse drug reactions and infections in the patients included in the safety analysis up to the time of approval will be summarized.

Line

No	Item name	Description
1	Number of patients included in the safety analysis	The number of patients included in the safety analysis will be counted.
2	Number of patients with adverse drug reactions	Adverse drug reactions reported up to the time of approval will be counted as the number of patients. If the same adverse drug reaction (PT) occurs repeatedly and is recorded multiple times, the adverse drug reaction will be counted once. Any event occurring beyond Week 52 will be excluded from the summarization for Attached Form 2.
3	Percentage of patients with adverse drug reactions	= Number of patients with adverse drug reactions / number of patients included in the safety analysis × 100
4	System organ class	MedDRA SOCs will be used. If the same patient experiences any adverse drug reaction (MedDRA SOC) multiple times, the patient will be counted once. Adverse drug reactions will be displayed in the order of SOC codes.
5	Event name	MedDRA PTs will be used. If the same patient experiences any adverse drug reaction (MedDRA PT) multiple times, each event will be counted once. Adverse drug reactions will be displayed in the order of PT codes.

4.7.1.2. Occurrence of adverse drug reactions and infections reported in post-marketing surveillance, etc. [Re-examination, Attached Form 15 (New notification)]

The occurrence of adverse drug reactions and infections in the patients included in the safety analysis reported in post-marketing surveillance, etc. will be summarized, as with Attached Form 2 (New notification).

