 - ⑤ Start date of administration,
- 3) In case any patient who had been administered with LipaCreon were enrolled, the information before the enrollment is to be collected as much as possible if it is required in the registry items.

(3) Observation Period

The observation period for a case is at least 52 weeks from the start of administration of LipaCreon. Even if the administration period exceeded 52 weeks, the assessment is to be done at the time of 52nd weeks. After 52nd week, administration status, concomitant use drug status, nutritious assessment items, symptoms relating to pancreatic excretion insufficiency and adverse events should be described in the Follow-up Case Report Form, and it should be submitted to the sponsor company.

(4) Description and submission of the Case Report Form

In this Registry, the Case Report Form is consisted of seven report brochures. After each whole follow-up period per case is completed, follow-up items should be fulfilled on all the registered cases (incl. discontinued cases). After all items were fulfilled, final confirmation date

should be written, signature should be done, and seal should be done before submission.

The Case Report Form (1): From the first administration date to 52nd week

The Case Report Form (2) – (7): After 52nd administration, one CRF per year

(5) Discontinued cases

In this Registry, the cases which the administration was discontinued during the observation period, or which follow-up became impossible due to patient's visit stopped, or other reasons, will be handled as "discontinued cases". For these discontinued cases, stopped date, reason of stopping, assessment done until the discontinuation should be written in the forms.

7. Planned registry period

Planned registry period: From the release of Lipa Creon to 31st March 2018

Case registration period: From the release of Lipa Creon to 31st March 2017

Observation period: For 52 weeks from the start of administration of LipaCreon. Even if the administration period exceeded 52 weeks, the assessment is to be done at the time of 52nd weeks.

Follow-up period: After the 52nd week, administration status, concomitant use drug status, nutritious assessment items, symptoms relating to pancreatic excretion insufficiency and adverse events should be described in the Follow-up Case Report Form annually, and it should be submitted to the company.

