1.2. Outline of the Survey

Brand name: Lipacreon® Granules 300 mg Sachets, Lipacreon® Capsules 150 mg

Survey name: Special Drug Use-Results Survey

CF all-case surveillance: P12-893/LPC02T

Special Drug Use-Results Survey (all-case surveillance) —All-Case Surveillance in Patients with Exocrine Pancreatic Insufficiency due to Cystic Fibrosis of the Pancreas—

Date of approval: April 22, 2011

Date of designation: April 14, 2011

End date of the re-examination period: April 21, 2019

Survey period: August 30, 2011 through March 31, 2018

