2.1. Definitions of Analysis Sets

No	Definition name	Description
1	Survey period	
Reporting interval for periodic safety reports
 
3rd: April 14, 2012 to October 13, 2012
 
4th: October 14, 2012 to April 13, 2013
 
5th: April 14, 2013 to April 13, 2014
 
6th: April 14, 2014 to April 13, 2015
 
7th: April 14, 2015 to April 13, 2016
 
8th: April 14, 2016 to April 13, 2017
 
9th: April 14, 2017 to April 13, 2018
 
10th: April 14, 2018 to April 13, 2019
 
End date of the re-examination period
 
April 21, 2019

2	Data lock dates	
The data lock date for periodic safety reports are as follows:
 
3rd: October 13, 2012
 
4th: April 13, 2013
 
5th: April 13, 2014
 
6th: April 13, 2015
 
7th: April 13, 2016
 
8th: April 13, 2017
 
9th: April 13, 2018
 
10th: April 17, 2019
 
The data lock date for re-examination is as follows:
 
April 17, 2019
 
At each analysis, the following case report forms will be analyzed:
 
Periodic safety report: Case report forms whose case report form status on each data lock date is “Primary data lock”
 
Analysis for re-examination: All case report forms whose case report form status is “Data lock”

3	Patients registered in the survey	Patients who have been able to be registered in the survey
4	Patients with available case report forms	Patients whose case report forms have been collected
5	Patients with no available case report forms	Patients whose case report forms have not been able to be collected
6	Criteria for exclusion from the safety analysis	
 ▪ No dose received: Patients whose use of Lipacreon has not been able to be confirmed ▪ No visit made: Patients who have not visited the institution since the start date of treatment with Lipacreon
7	Patients excluded from the safety analysis	Patients meeting the criteria for exclusion from the safety analysis among the patients with available case report forms
8	Patients included in the safety analysis	Patients not meeting the criteria for exclusion from the safety analysis among the patients with available case report forms

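### The re-examination form for adverse drug reactions up to approval is built on the survey's own safety set, which did not exist at approval, and no pre-approval data source is named

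*SAP*

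**What the plan says.** SAP 4.7 opens with one patient statement for all three of its forms: "Patients for summarization: Patients with available case report forms and patients included in the safety analysis". Section 4.7.1.1 then sets out Attached Form 2 (New notification).

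- **Scope:** "The occurrence of adverse drug reactions and infections in the patients included in the safety analysis up to the time of approval will be summarized".
- **Denominator (line 1):** the number of patients included in the safety analysis.
- **Numerator (line 2):** "Adverse drug reactions reported up to the time of approval will be counted as the number of patients". The same line drops events after Week 52 from Attached Form 2.
- **Percentage (line 3):** "Number of patients with adverse drug reactions / number of patients included in the safety analysis × 100".

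SAP 2.1 No. 8 defines the safety set as "Patients not meeting the criteria for exclusion from the safety analysis among the patients with available case report forms". SAP 2.1 No. 2 makes the locked case report forms the input for the re-examination analysis. SAP 2.2 Nos. 11 and 13 define ADRs as a subset of the events entered in the adverse event column of those forms.

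The dates are in SAP 1.2: "Date of approval: April 22, 2011" and "Survey period: August 30, 2011 through March 31, 2018". Protocol section 7 agrees on the order of events: "Case registration period: From the release of Lipa Creon to 31st March 2017".

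SAP 4.7.1.2 (Attached Form 15) covers ADRs from post-marketing surveillance. It names the same safety set and says only that the tabulation follows Attached Form 2 (New notification).

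**The concern.** The title of the form points to the period before approval, while every defined term in it points to patients enrolled afterwards. The numerator condition and the patient set hardly overlap, if at all. A programmer who follows the SAP would print a row of zeros over the survey denominator. One who departs from it would have to choose a data source and a denominator that the plan does not give.

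At stake is the one table in the SAP labelled as showing pre-approval ADR incidence. A 0.00% there would be read as a finding from the pre-approval studies, when it only reflects the order of two dates. Form 15 is also exposed, because its rules are given only by reference to this form.

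**Working it through.** The plan states no figure to reproduce here, so the check is calendar arithmetic followed by the SAP's own percentage rule.

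**1. Gap between approval and survey start (SAP 1.2).** From 22 April to 30 August 2011: 8 (rest of April) + 31 + 30 + 31 + 30 = 130 days.

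**2. Numerator under line 2.** It takes ADRs in the survey safety set reported by 22 April 2011. Survey reporting begins 130 days after that date, so the count is 0.

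**3. Percentage under line 3.** 0 / N × 100 = 0.00% for any safety-set size N, and for every SOC and PT. N is not given, and the result does not depend on it.

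**4. Does the SAP provide for treatment starting before approval?** The survey runs from 30 August 2011 to 31 March 2018, which is 2406 days inclusive. The SAP's last dose and onset categories end at Day 2400, close to that length. A patient treated continuously from the approval date would reach Day 2406 + 130 = 2536, outside every category. The categories were evidently drawn for starts within the survey.

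**5. Sensitivity to a carried-over patient.** Protocol 6(2) 3) collects pre-enrolment information on patients already given the drug. Suppose that "up to approval" is judged by onset date, not report date, and that one survey patient had an ADR in a pre-approval study. The result is then 1/N. Taking as an assumption N = 13 or N = 38 (the national patient counts in Protocol section 2):

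| Assumed N | As written | One carried-over patient |
|---|---|---|
| 13 | 0/13 = 0.00% | 1/13 = 7.7% |
| 38 | 0/38 = 0.00% | 1/38 = 2.6% |

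Neither column is the pre-approval study incidence, since the denominator is still the survey's.

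**6. The Week 52 exclusion.** If only reports made by approval count, in a survey that began later, this exclusion has nothing to remove. It has content only if line 2 covers other patients, or if it passes to Form 15 through the cross-reference in 4.7.1.2. In the latter case, for a patient followed to Day 2400, the share of follow-up left out of Form 15 would be (2400 − 364) / 2400 = 2036 / 2400 = 84.8%.

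**7. Is the gap filled elsewhere?** The SAP leaves the contents of Forms 3 and 16 to a separate specification (4.6.1.3 and 4.7.1.3). It makes no such deferral for this form, and it defines no pre-approval data set, safety population or source. The protocol says only that few patients were enrolled in the domestic studies. No corrected incidence can therefore be calculated.

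**The case against.** The strongest reply is that nobody would run survey patients through a form with this title. The scope sentence can be read as meaning the safety population studied up to approval, and it is set apart from Form 15, which is expressly post-marketing. The patient statement in 4.7 serves three forms, and Forms 15 and 16 alone could account for both sets listed. On this view the plan merely omits a data source.

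The point about intent stands: the pre-approval studies are probably meant. It does not remove the defect. The phrase used is a defined term with one definition, the header applies it to the whole of 4.7, and intent supplies neither a data set nor a denominator.

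Three further limits also stand.

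- A reader might infer that a false 0% would make every survey ADR look new or increased. The documents do not support that. For Attached Form 2 in SAP 4.6.1.1, whether an ADR is unknown is decided from separate novelty information supplied by the sponsor.
- A reader might link this form to Protocol 13(2) 3), which lists a problem found in comparison with results up to approval as a reason to consider further study. Neither document says that this form feeds that comparison.
- A reader might assign the Week 52 exclusion to the pre-approval studies. No document gives their duration or says that the rule was written for them.

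**Conclusion.** The point holds as a mismatch between the form's purpose and its stated population. Followed literally, SAP 4.7.1.1 yields essentially 0/N over the survey safety set and not the pre-approval ADR incidence. The 130-day gap is exact. The zero rests on line 2's wording about when a reaction was reported, and on there being no patient carried over from a pre-approval study. The documents record no such patient.

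The effect is limited to this form, which is produced only at re-examination, and possibly to Form 15 if the Week 52 exclusion passes to it. The survey's own safety tables in SAP 4.2 keep their correct denominator. It should be corrected before the re-examination tables are programmed, because the form cannot be produced correctly from the current text.

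**What to change.** 1. In SAP 4.7 and 4.7.1.1, name the pre-approval clinical study data set that feeds Attached Form 2 (New notification), and use that data set's own safety population for lines 1 to 3.
2. Keep the SAP 2.1 No. 8 survey set for Attached Form 15, and say so in 4.7.1.2.
3. State which form the Week 52 exclusion governs. In particular, make clear that the cross-reference in 4.7.1.2 does not remove survey ADRs after Week 52 from Form 15, unless that is intended.

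The cost in the SAP is a few lines of wording, with no change to survey data collection. Whether a suitable pre-approval tabulation already exists cannot be told from the documents. If it does not, the sponsor would have to prepare one from the study data.
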